# 8.1.2. Collection and Reporting Serious Adverse Events

Following the subject's written consent to participate in the study, all SAEs, whether related or not related to study drug, must be collected, including those thought to be associated with protocol-specific procedures. All SAEs must be collected that occur from the time the informed consent form (ICF) is signed and throughout the course of the study up to and including the End of Treatment Visit. The investigator should report any SAE occurring after this time period that is believed to be related to study drug or protocol-specific procedures.

All SAEs should be followed to resolution or stabilization.

An SAE report should be completed for any event where doubt exists regarding its status of seriousness.

If the investigator believes that an SAE is not related to the study drug, but is potentially related to the conditions of the study (such as a withdrawal of previous therapy or a complication related to study procedure), the relationship should be specified in the narrative Section of the SAE Report.

SAEs, whether related or not related to study drug, overdose (see Section 8.3), potential drug induced liver injury (see Section 8.4) and pregnancies (see Section 8.5.1) must be reported within 24 hours of the Investigator becoming aware of the event. For this study, SAEs will be captured through EDC and on the SAE report.

The Investigator is responsible for submitting all applicable events to the Independent Review Board (IRB) and/or the head of the institutional site as per the IRB's reporting requirements. Additionally, the Investigator, or designated staff, is responsible for entering the SAE information into the Case Report Form (CRF) and safety reporting system (i.e.: event term, start stop dates, causality, severity).

The Investigator is responsible for reporting all SAEs and all Other Important Medical Events to the Pfizer Drug Safety Unit (DSU) within 24 hours of learning of the event.

Any serious adverse event must be reported immediately or no later than 24 hours after awareness of the event to Pfizer DSU either via the Pfizer SAE Submission Assistant (PSSA) tool or as a written description using the Pfizer CT SAE report, that must be sent by facsimile (fax or eFax) or email to the Pfizer DSU on [name] or [name].

If only limited information is initially available, follow-up reports are required. If an ongoing SAE changes in its intensity or relationship to study drug or if new information becomes available, a follow-up SAE report should be sent within 24 hours of the Investigator becoming aware of the updated information using the same procedure used for the transmission of the initial SAE and the same event term should be used.

The minimum information required for an initial SAE report is:

Sender of report (Site number, Investigator name)

Subject identification (subject number)

Protocol number

SAE term (if an SAE is being reported)

#### 8.2. Non-serious Adverse Events

A non-serious adverse event is an AE not classified as serious.

#### 8.2.1. Collection and Reporting of Non-Serious Adverse Events

The collection of non-serious AE information should begin at the Baseline Visit through the End of Treatment Visit.

Non-serious AEs should be followed until conclusion or stabilization, or reported as SAEs if they become serious. Follow-up is also required for non-serious AEs that cause interruption or discontinuation of study drug or those that are present at the end of study treatment.

# 8.2.2. Laboratory Test Abnormalities

The following laboratory test abnormalities should be captured on the non-serious AE CRF page or SAE Report Form (paper or electronic) as appropriate:

- 1. Any laboratory test result that is clinically significant or meets the definition of an SAE;
- 2. Any laboratory abnormality that required the subject to have the study drug discontinued or interrupted;
- 3. Any laboratory abnormality that required the subject to receive specific corrective therapy.

# 8.3. Overdose

An overdose is defined as the accidental or intentional administration of any dose of the product that is considered both excessive and medically important as determined by the investigator.

Overdose is reportable to Pfizer Safety only when associated with an SAE. Details of any signs or symptoms and their management should be recorded including details of any antidote(s) administered.

Asymptomatic dosing errors should be reported as deviations.

# 8.4. Potential Drug Induced Liver Injury (DILI)

Humans exposed to a drug who show no sign of liver injury (as determined by elevations in transaminases) are termed "tolerators," while those who show transient liver injury but adapt are termed "adaptors." In some subjects, transaminase elevations are a harbinger of a more serious potential outcome. These subjects fail to adapt and therefore are "susceptible" to progressive and serious liver injury, commonly referred to as DILI. Subjects who experience a transaminase elevation above  $3 \times$  ULN should be monitored more frequently to determine if they are "adaptors" or are "susceptible."

In the majority of DILI cases, elevations in AST and/or ALT precede T bili elevations (> $2 \times$  ULN) by several days or weeks. The increase in T bili typically occurs while AST/ALT is/are still elevated above  $3 \times$  ULN (ie, AST/ALT and T bili values will be elevated within the same laboratory sample). In rare instances, by the time T bili elevations are detected, AST/ALT values might have decreased. This occurrence is still regarded as a potential DILI. Therefore, abnormal elevations in either AST OR ALT in addition to T bili that meet the criteria outlined below are considered potential DILI (assessed per Hy's law criteria) cases and

should always be considered important medical events, even before all other possible causes of liver injury have been excluded.

The threshold of laboratory abnormalities for a potential DILI case depends on the subject's individual baseline values and underlying conditions. Subjects who present with the following laboratory abnormalities should be evaluated further as potential DILI (Hy's law) cases to definitively determine the etiology of the abnormal laboratory values:

- Subjects with AST/ALT and T bili baseline values within the normal range who subsequently present with AST OR ALT values ≥3 × ULN AND a T bili value ≥2 × ULN with no evidence of hemolysis and an alkaline phosphatase value <2 × ULN or not available.
- For subjects with baseline AST **OR** ALT **OR** T bili values above the ULN, the following threshold values are used in the definition mentioned above, as needed, depending on which values are above the ULN at baseline:
  - Preexisting AST or ALT baseline values above the normal range: AST or ALT values ≥2 times the baseline values AND ≥3 × ULN; or ≥8 × ULN (whichever is smaller).
  - Preexisting values of T bili above the normal range: T bili level increased from baseline value by an amount of ≥1 × ULN or if the value reaches ≥3 × ULN (whichever is smaller).

Rises in AST/ALT and T bili separated by more than a few weeks should be assessed individually based on clinical judgment; any case where uncertainty remains as to whether it represents a potential Hy's law case should be reviewed with the sponsor. The subject should return to the investigator site and be evaluated as soon as possible, preferably within 48 hours from awareness of the abnormal results. This evaluation should include laboratory tests, detailed history, and physical assessment.

In addition to repeating measurements of AST and ALT and T bili for suspected Hy's law cases, additional laboratory tests should include albumin, CK, direct and indirect bilirubin, GGT, PT/INR, eosinophils (%), and alkaline phosphatase. Consideration should also be given to drawing a separate tube of clotted blood and an anticoagulated tube of blood for further testing, as needed, for further contemporaneous analyses at the time of the recognized initial abnormalities to determine etiology. A detailed history, including relevant information, such as review of ethanol, acetaminophen/paracetamol (either by itself or as a coformulated product in prescription or over-the-counter medications), recreational drug, or supplement (herbal) use and consumption, family history, sexual history, travel history, history of contact with a jaundiced person, surgery, blood transfusion, history of liver or allergic disease, and potential occupational exposure to chemicals, should be collected. Further testing for acute hepatitis A, B, C, D, and E infection, total bile acids, liver imaging (eg, biliary tract), and collection of serum samples for acetaminophen/paracetamol drug and/or protein adduct levels may be warranted.

All cases demonstrated on repeat testing as meeting the laboratory criteria of AST/ALT and T bili elevation defined above should be considered potential DILI (Hy's law) cases if no

# other reason for the LFT abnormalities has yet been found. Such potential DILI (Hy's law) cases are to be reported as SAEs, irrespective of availability of all the results of the investigations performed to determine etiology of the LFT abnormalities.

A potential DILI (Hy's law) case becomes a confirmed case only after all results of reasonable investigations have been received and have excluded an alternative etiology.

# **8.5.** Environmental Exposure, Exposure During Pregnancy or Breastfeeding, and Occupational Exposure

Environmental exposure occurs when a person not enrolled in the study as a subject receives unplanned direct contact with or exposure to the study intervention. Such exposure may or may not lead to the occurrence of an AE or SAE. Persons at risk for environmental exposure include healthcare providers, family members, and others who may be exposed. An environmental exposure may include EDP, EDB, and occupational exposure.

Any such exposures to the study intervention under study are reportable to Pfizer Safety within 24 hours of investigator awareness.

# 8.5.1. Exposure During Pregnancy

If following the baseline visit, it is subsequently discovered that a study subject, or the female partner of a male study subject, is pregnant or may have been pregnant at the time of the investigational product exposure, including during at least 6 half-lives after the product administration, the investigational product will be permanently discontinued in an appropriate manner (i.e., dose tapering if necessary for subject's safety). Protocol-required procedures for the study discontinued and the follow-up must be performed on the subject unless contraindicated by the pregnancy (ie, x-ray studies). Other appropriate pregnancy follow-up procedures should be considered if indicated.

Sites should instruct subjects to contact the Investigator if they become pregnant during the course of the study. The investigator must immediately notify the Pfizer Medical Monitor (or designee) and report the event to the Pfizer DSU by either using the PSSA tool or by completing an EDP Supplemental Form and following the SAE reporting procedures as described in Section 8.1.2.

Follow-up information regarding the course of the pregnancy, including perinatal and neonatal outcome and, where applicable offspring information must also be reported as described above.

Any pregnancy that occurs in a female partner of a male study subject should be reported to the Pfizer DSU. Information on this pregnancy will be collected as described above.

An EDP occurs if:

- A female subject is found to be pregnant while receiving or after discontinuing study intervention.
- A male subject who is receiving or has discontinued study intervention inseminates a female partner.

- A female nonsubject is found to be pregnant while being exposed or having been exposed to study intervention because of environmental exposure. Below are examples of environmental EDP:
  - A female family member or healthcare provider reports that she is pregnant after having been exposed to the study intervention by ingestion or skin contact.
  - A male family member or healthcare provider who has been exposed to the study intervention by ingestion or skin contact then inseminates his female partner prior to or around the time of conception.

The investigator must report EDP to Pfizer Safety within 24 hours of the investigator's awareness, irrespective of whether an SAE has occurred. The initial information submitted should include the anticipated date of delivery (see below for information related to termination of pregnancy).

- If EDP occurs in a subject/subject's partner, the investigator must report this information to Pfizer Safety using the CT SAE Report Form or via PSSA, regardless of whether an SAE has occurred. Details of the pregnancy will be collected after the start of study intervention and until 66 hours after the last dose.
- If EDP occurs in the setting of environmental exposure, the investigator must report information to Pfizer Safety using the CT SAE Report Form or via PSSA. Since the exposure information does not pertain to the subject enrolled in the study, the information is not recorded on a CRF; however, a copy of the completed report is maintained in the investigator site file.

Follow-up is conducted to obtain general information on the pregnancy and its outcome for all EDP reports with an unknown outcome. The investigator will follow the pregnancy until completion (or until pregnancy termination) and notify Pfizer Safety of the outcome as a follow-up to the initial report. In the case of a live birth, the structural integrity of the neonate can be assessed at the time of birth. In the event of a termination, the reason(s) for termination should be specified and, if clinically possible, the structural integrity of the terminated fetus should be assessed by gross visual inspection (unless pre-procedure test findings are conclusive for a congenital anomaly and the findings are reported).

Abnormal pregnancy outcomes are considered SAEs. If the outcome of the pregnancy meets the criteria for an SAE (ie, ectopic pregnancy, spontaneous abortion, intrauterine fetal demise, neonatal death, or congenital anomaly in a live born baby, a terminated fetus, an intrauterine fetal demise, or a neonatal death), the investigator should follow the procedures for reporting SAEs. Additional information about pregnancy outcomes that are reported to Pfizer Safety as SAEs follows:

- Spontaneous abortion including miscarriage and missed abortion should be reported as an SAE;
- Neonatal deaths that occur within 1 month of birth should be reported, without regard to causality, as SAEs. In addition, infant deaths after 1 month should be reported as SAEs

when the investigator assesses the infant death as related or possibly related to exposure to the study intervention.

Additional information regarding the EDP may be requested by the sponsor. Further follow-up of birth outcomes will be handled on a case-by-case basis (eg, follow-up on preterm infants to identify developmental delays). In the case of paternal exposure, the investigator will provide the subject with the Pregnant Partner Release of Information Form to deliver to his partner. The investigator must document in the source documents that the subject was given the Pregnant Partner Release of Information Form to provide to his partner.

# 8.5.2. Exposure During Breastfeeding

An EDB occurs if:

- A female subject is found to be breastfeeding while receiving or after discontinuing study intervention.
- A female nonsubject is found to be breastfeeding while being exposed or having been exposed to study intervention (ie, environmental exposure). An example of environmental EDB is a female family member or healthcare provider who reports that she is breastfeeding after having been exposed to the study intervention by ingestion.

The investigator must report EDB to Pfizer Safety within 24 hours of the investigator's awareness, irrespective of whether an SAE has occurred. The information must be reported using the CT SAE Report Form or via PSSA. When EDB occurs in the setting of environmental exposure, the exposure information does not pertain to the subject enrolled in the study, so the information is not recorded on a CRF. However, a copy of the completed report is maintained in the investigator site file.

An EDB report is not created when a Pfizer drug specifically approved for use in breastfeeding women (eg, vitamins) is administered in accordance with authorized use. However, if the infant experiences an SAE associated with such a drug, the SAE is reported together with the EDB.

# 8.5.3. Occupational Exposure

The investigator must report any instance of occupational exposure to Pfizer Safety within 24 hours of the investigator's awareness using the CT SAE Report Form or via PSSA, regardless of whether there is an associated SAE. Since the information about the occupational exposure does not pertain to a subject enrolled in the study, the information is not recorded on a CRF; however, a copy of the completed report is maintained in the investigator site file.

# 8.6. Lack of Efficacy

The investigator must report signs, symptoms, and/or clinical sequelae resulting from lack of efficacy. Lack of efficacy or failure of expected pharmacological action is reportable to Pfizer Safety **only if associated with an SAE**.

# 8.7. Medication Errors

Medication errors may result from the administration or consumption of the study intervention by the wrong subject, or at the wrong time, or at the wrong dosage strength.

Recorded on the Medication Error Page of the CRF	Recorded on the Adverse Event Page of the CRF	Reported on the CT SAE Report Form or PSSA to Pfizer Safety Within 24 Hours of Awareness
All (regardless of whether associated with an AE)	Any AE or SAE associated with the medication error	Only if associated with an SAE

Medication errors are recorded and reported as follows:

# 8.8. Adverse Events of Special Interest

Not applicable for this study.

# 9. STATISTICS

Complete details on the statistical methods for this study may be found in the Statistical Analysis Plan (SAP).

# 9.1. Sample Size

This study will randomize a total of 795 subjects in a 1:1:1 ratio to rimegepant 25 mg, rimegepant 75 mg, or placebo. It is anticipated that this will result in approximately 750 subjects in efficacy analysis set, with roughly 250 subjects in each treatment arm.

Although testing strategy is changed in Protocol version 4.0 and formal hypothesis testing will no longer be conducted for rimegepant 25 mg, the original sample size will remain as it is. The sample size for this study was designed to provide 80% power to test each of the 2 rimegepant doses against placebo at a Bonferroni corrected 2-sided alpha level of 0.025 using a chi-square test. The sample size estimate is based on historical data from pivotal study BHV3000-303, in which the rates of pain freedom were 10.9% for placebo and 21.2% for Rimegepant.

# 9.2. Analysis Set

The following analysis sets will be used for statistical analyses, as applicable:

- Enrolled: Subjects who sign an ICF and are assigned a subject identification number.
- Full: Subjects in the enrolled analysis set who receive a randomization treatment assignment from the IWRS (rimegepant 25 mg, 75 mg or placebo).
- Safety: Subjects in the enrolled analysis set who take study therapy (rimegepant 25 mg, rimegepant 75 mg, or placebo).
- Efficacy: Subjects in the full analysis set who are randomized only once, take study therapy, have a migraine of moderate or severe pain intensity at the time of treatment, and provide at least one post-dose efficacy data point.

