- Freedom from nausea at 2 hours post-dose will be assessed using the percentage of subjects with nausea absent at 2 hours post-dose in the subset of subjects with nausea present at the time of dosing.
- Pain relapse from 2 to 48 hours post-dose will be assessed using the percentage of subjects with a pain intensity of mild, moderate, or severe at any time point after 2 hours through 48 hours post-dose in the subset of subjects with pain freedom at 2 hours post-dose.
- Tolerability and safety will be evaluated by the percentage of subjects with AEs by intensity, SAEs, and grade 3 to 4 laboratory test abnormalities.

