#### 6.3.3. Rescue Medication

The subject's use of rescue medication is recorded by the subject in a paper diary.

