# 7.4. Treatment Compliance

Responsible study personnel will dispense the study drug. Accountability and compliance verification should be documented in the subject's study records.

Subjects will be counseled on the importance of taking the study drug as directed when a migraine occurs and reaches moderate or severe intensity. If the subject does not have a

migraine or take their study drug within 45 days of the Baseline Visit, they should return to the clinic for their End of Study Visit and return their unused study drug.

Subjects who take study drug will be asked to return all empty blister packaging and wallets to the study site at the End of Study Visit.

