# 9.3.2. Primary Endpoint(s)

BHV-3000 (rimegepant) 75 mg is tested for superiority to placebo, at a 2-sided alpha level of 0.05, on the primary endpoint of pain freedom at 2 hours post-dose. For rimegepant 25 mg, formal hypothesis testing will not be conducted, and the nominal p-value will be provided only for descriptive purposes.

The endpoint will be evaluated using Mantel-Haenszel risk estimation with stratification by the use of prophylactic migraine medication (yes or no) for the efficacy analysis set. The difference estimate (rimegepant – placebo), 95% CI, and p-value will be reported for each rimegepant treatment group versus placebo. Subjects with missing data at 2 hours post-dose will be imputed to be failure (i.e., Non-completer = Failure; NC=F).

Subjects who use rescue medication at or before the assessment of their primary endpoint will be classified as failures. Sensitivity analyses are described in the Statistical Analysis Plan (SAP).

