# 9.3.3. Secondary Endpoint(s)

The same statistics for secondary endpoints (as listed in Section 3.2) will be presented as those for the primary endpoint.

For endpoints based on a single time point, such as pain freedom at 2 hours post-dose, subjects with missing data at a single time point will be classified as failures (NC=F). For endpoints based on multiple time points, such as sustained pain relief from 2 to 48 hours post-dose, subjects with missing data at (1) 2, 24, or 48 hours post-dose, or (2) more than 1 time point from 3 to 8 hours post-dose will also be classified as failures.

For all secondary endpoints except the rescue medication use within 24 hours post-dose, subjects who use rescue medication at or before the assessment of their endpoint will be classified as failures.

See section 9.3.5 for safety endpoints.

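### The efficacy set drops a treated subject who records nothing after dosing, so NC=F cannot count that subject as a failure; secondarily, pain relapse is formally tested in a subset that treatment affects

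*Protocol*

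**What the plan says.** **Analysis set.** Protocol 9.2 builds the efficacy set from subjects randomised only once who take study therapy for a migraine of moderate or severe intensity. It then adds a last condition: "and provide at least one post-dose efficacy data point". Section 9.3.2 runs the primary analysis on this set and states: "Subjects with missing data at 2 hours post-dose will be imputed to be failure". Section 9.3.3 repeats the rule for secondary endpoints at a single time point. The term efficacy data point is not defined. Rescue use is listed under Efficacy Assessments, but 6.3.3 says that the "use of rescue medication is recorded by the subject in a paper diary", not in the eDiary, so it is unclear whether a rescue record alone admits a subject.

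**Planned numbers.** Section 9.1 randomises 795 and anticipates "approximately 750 subjects in efficacy analysis set, with roughly 250 subjects in each treatment arm". The shortfall is not split by reason. It must include subjects who never dose, since 7.4 provides for those who do not have a "migraine or take their study drug within 45 days of the Baseline Visit".

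**Pain relapse.** Section 3.2 defines it "in the subset of subjects with pain freedom at 2 hours post-dose". It is the last of 12 secondary efficacy endpoints in 2.2, and 9.3.4 tests these for 75 mg in that order at alpha 0.05, with no exception for relapse. The other restricted endpoints (most bothersome symptom, function, photophobia, phonophobia, nausea) use status before or at dosing.

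**Sensitivity analyses.** Section 9.3.2 leaves these to the SAP. The SAP supplied is for C4951021, a migraine-prevention trial.

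**The concern.** (a) NC=F is the protocol's chosen protection against missing outcomes, but the entry condition switches it off where missingness is complete. The condition is observed after randomisation and after dosing. If total non-response differs between arms, the primary comparison is no longer between everyone who treated a qualifying attack as randomised.

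(b) Pain freedom at 2 hours is the primary outcome, and the trial expects the drug to raise it. The 2-hour responders on drug therefore include people who would not have responded on placebo. A difference in relapse between the two responder groups can reflect that mix and not any effect of the drug on relapse. At stake is only what the relapse p-value means: whether a significant result could support a formal claim.

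**Working it through.** **1. The plan's own figure.** Inputs from 9.1: 10.9% versus 21.2%, 250 per arm, 2-sided alpha 0.025, chi-square test.
- Null SE = sqrt(2 × 0.1605 × 0.8395 / 250) = 0.0328.
- Alternative SE = sqrt((0.212 × 0.788 + 0.109 × 0.891) / 250) = 0.0325.
- Power = Φ((0.103 − 2.241 × 0.0328) / 0.0325) = 81.7%, which agrees with the stated 80%.
- At the current alpha of 0.05 (1.960 in place of 2.241), power is 88.3%.

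**2. How many subjects.** (795 − 750) / 3 = 15 per arm on average. This comes from approximate planning figures, covers all reasons including never dosing, and does not limit the number or its split by arm. The number treated with no post-dose data is not given, so a range is used.

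**3. Power with those subjects counted as failures.** Each rate becomes rate × 250/(250 + k), alpha 0.05:

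| Failures added (75 mg / placebo) | Power |
|---|---|
| 0 / 0 | 88.3% |
| 5 / 5 | 88.2% |
| 10 / 10 | 88.0% |
| 15 / 15 | 87.9% |
| 15 / 0 | 81.6% |

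**4. Borderline results.** Unstratified risk difference, unpooled SE:

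| 75 mg | Placebo | p |
|---|---|---|
| 43/250 | 27/250 | 0.038 |
| 43/256 (6 added) | 27/250 | 0.049 |
| 43/257 (7 added) | 27/250 | 0.0515 |
| 43/257 (7 added) | 27/257 (7 added) | 0.039 |
| 44/250 | 27/250 | 0.029 |
| 44/260 (10 added) | 27/250 | 0.044 |
| 45/250 | 27/250 | 0.021 |
| 45/265 (15 added) | 27/250 | 0.041 |

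The window is narrow, and it needs exclusions concentrated in the active arm.

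**5. Relapse subset.** 250 × 0.212 = 53 on 75 mg; 250 × 0.109 = 27.25 on placebo.

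**6. What selection can do.** Assume that every placebo responder would also respond on drug, and that the drug does not alter relapse. Then relapse in the drug arm = (0.109 × shared + 0.103 × drug-only) / 0.212, where shared and drug-only are the relapse rates in those who respond either way and in those who respond only on drug. The documents give no relapse rates, so these are assumptions.
- Shared 60%, drug-only 40%: (0.0654 + 0.0412) / 0.212 = 50.3% against 60% on placebo, an apparent benefit of 9.7 points.
- Shared 40%, drug-only 60%: (0.0436 + 0.0618) / 0.212 = 49.7% against 40%, an apparent harm of 9.7 points.

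**7. How often the formal test would be falsely favourable.** 1,000,000 simulated trials per case, 250 per arm, no missing data or rescue, unstratified 2-sided 0.05 z tests. The primary and sustained pain freedom 2–48 h must both be significant first, which is two of the 12 earlier tests.

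| Shared / drug-only relapse | Pooled SE | Unpooled SE |
|---|---|---|
| 40 / 40 | 2.3% | 2.4% |
| 60 / 60 | 2.2% | 3.0% |
| 50 / 40 | 5.5% | 6.1% |
| 60 / 50 | 5.3% | 6.6% |
| 40 / 20 | 12.8% | 12.1% |
| 50 / 30 | 11.7% | 12.3% |
| 60 / 40 | 11.3% | 13.0% |
| 60 / 30 | 20.7% | 22.7% |

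The unpooled SE is closer to the planned Mantel-Haenszel risk difference. If drug-only responders relapse 10 to 40 points more, a formal result in the wrong direction occurs in 0.3% to 4.8% of trials (pooled) or 0.5% to 7.7% (unpooled).

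**The case against.** On (a): one post-dose entry is enough for admission, and 12 eDiary time points are scheduled. A subject with any of them but no 2-hour value is already a failure. Nothing in a double-blind, double-dummy trial suggests that total non-response would differ by arm. The trial's own SAP may define the data point or plan a broader-set analysis. All of this stands and makes the point minor. It does not remove the inconsistency, because the primary set itself is fixed in the protocol.

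A reader might take 15 per arm as the most that could be excluded, or infer that the primary result is materially biased. The documents support neither: 15 is an average of approximate planning figures, and the calculations show little effect in most scenarios.

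On (b): relapse is last, so it passes alpha to nothing, and a prespecified final conditional endpoint can be defended. Against the literal null of equal relapse proportions among 2-hour responders, the test behaves about as intended: 2% to 3% falsely favourable, near the nominal one-sided 2.5%. The larger rates are false only against a null about the drug's effect on relapse. They rest on assumed gaps and on the assumption about placebo responders, and further gates could only lower them. They are not this trial's error rate.

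A reader might also call relapse redundant, since its count equals 2-hour pain-free subjects minus those with sustained pain freedom. That goes too far. The relapse proportion among responders is a separate question, and sustained pain freedom mixes response with durability.

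**Conclusion.** Both points hold, as modest improvements.

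(a) The clause removes from the primary denominator exactly the treated subjects that NC=F should count as failures. The expected effect is small: power changes by 0.4 points with 15 failures added to each arm, and significance is lost only in a borderline result with unequal exclusions. This rests on the 9.1 planning rates and an assumed number of affected subjects. Whether this trial's SAP already plans a broader-set analysis cannot be checked.

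(b) The relapse p-value compares groups formed after dosing, so it should not support a formal claim about the drug's effect on relapse. The direction and size of any distortion are unknown. Under assumed gaps of 10 to 30 points less relapse in drug-only responders, falsely favourable results range from about 5% to 23%, against about 2% to 3% with equal relapse. The error rates of the primary and all other secondary tests are untouched.

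**What to change.** **Protocol 9.2.** Delete the final condition, so that NC=F covers every once-randomised subject who takes study therapy for a moderate or severe migraine. Report by arm how many had no post-dose data. At a minimum, prespecify this as a named sensitivity analysis of the primary endpoint. If the condition is kept, define the data point and say whether a paper rescue record counts.

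**Protocol 9.3.4.** State that pain relapse is outside the formal hierarchy and is reported descriptively, with a caveat that its subset is affected by treatment. Sustained pain freedom 2–24 h and 2–48 h, already 8th and 10th in the order, give the randomised comparison of durable response, but they do not estimate the relapse proportion.

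**Cost.** No new data are needed. Changing the primary set and the hierarchy is a protocol amendment requiring IRB/IEC approval (Section 12). Response rates would be slightly lower: with 15 added per arm, 53/265 = 20.0% and 27.25/265 = 10.3%, a difference of 9.7 points in place of 10.3. The sponsor gives up a formal relapse claim.
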